**Table 5.2: Vaccination, BL, and urinalysis schedule: the Russian Federation (Groups 3 and 4)**

Visit (V)	V0	V01	V02	V03	V04	V05	V06	V07
Subject Age	2 months	2 months	3 months	4.5 months	6 months	7 months	12 months	13 months
Group 3	BL0001 (6 mL) UA (8 mL)	Pprevnar 13 ®†	MenACYW* Pentaxim ®‡	Pprevnar 13 ®† Pentaxim ®‡	MenACYW* Pentaxim ®‡ ENGERIX-B ®§	BL0002 (6 mL)	MenACYW* MMR**	BL0003 (6 mL) UA (8 mL)
Group 4	BL0001 (6 mL) UA (8 mL)	Pprevnar 13 ®†	Pentaxim ®‡	Pprevnar 13 ®† Pentaxim ®‡	Pentaxim ®‡ ENGERIX-B ®§	BL0002 (6 mL)	MMR**	BL0003 (6 mL) UA (8 mL)

V: Visit, UA: Urinalysis

\*MenACYW conjugate vaccine

† No immunogenicity endpoints will be measured for this vaccine in the Russian Federation. The PCV13 routine vaccine recommended at 15 months of age in the Russian Federation is considered as out of scope for this study and will not be provided by the Sponsor but procured by the sites as per their standard practices.

‡ The 4th dose of Pentaxim®, which is administered at 18 months of age, is considered out of the scope of the study, and it will not be provided by the Sponsor but procured by the sites as per their standard practices. Subjects will be instructed to receive it for completion of the Pentavalent series as per the NIC of the Russian Federation recommendation.

§ In the event ENGERIX B® cannot be supplied in the Russian Federation, a locally licensed monovalent hepatitis B vaccine will be administered instead. Further details will be provided in the CSR.

\*\* In the event M-M-R®II combination vaccine cannot be supplied or is unavailable in the Russian Federation, locally licensed MMR or MM+R vaccines will be administered instead. Further details will be provided in the CSR.

**Table 5.3: Schedule of antigen testing: Mexico (Groups 1 and 2)**

Visit (V)	V01	V02	V03	V04	V05	V06
Subject Age	2 months	4 months	6 months	7 months	12 months	13 months
Trial Timeline	D0	V01 + 60 days	V02 + 60 days	V03 + 30 days	V04 + 150 to 180 days	V05 + 30 days
BL (5 mL)	BL0001			BL0002		BL0003
Group 1	Meningococcal Serogroups (A, C, Y, W)* Pertussis (PT, FHA) RV IgA	—	—	Meningococcal Serogroups (A, C, Y, W) PCV13 RV IgA		Meningococcal Serogroups (A, C, Y, W) PCV13 Hib (PRP) Pertussis (PT, FHA) HepB Polio (types 1, 2, 3) Tetanus Diphtheria M-M-R®II

Group 2
	
Meningococcal Serogroups (A, C, Y, W) Pertussis (PT, FHA) RV IgA
	
—
	
—
	
Meningococcal Serogroups (A, C, Y, W) PCV13 RV IgA
		
Meningococcal Serogroups (A, C, Y, W) PCV13 Hib (PRP) Pertussis (PT, FHA) HepB Polio (types 1, 2, 3) Tetanus Diphtheria M-M-R®II

-----------------------	---	----------	----------	---	--	--

PT: pertussis toxin; FHA: filamentous hemagglutinin; Hib: *Haemophilus influenzae* type B; PRP: polyribosyl-ribitol phosphate; HepB: hepatitis B; PCV13: pneumococcal 13-valent conjugate vaccine; M-M-R®II: measles, mumps, and rubella

\*Antibody responses to meningococcal serogroups (A, C, Y, and W) will be measured by rSBA before the first vaccination (Visit 1), 30 days after the final vaccination in the infant series, and 30 days after the last vaccination in the entire 3- or 4- dose vaccine schedule in a subset of subjects (100 subjects per group in Groups 1, 3, and 5 and 50 subjects per group in Groups 2, 4, and 6.)

**Table 5.4: Schedule of antigen testing: the Russian Federation (Groups 3 and 4)**

Visit (V)	V0	V01	V02	V03	V04	V05	V06	V07
Subject Age	2 months	2 months	3 months	4.5 months	6 months	7 months	12 months	13 months
Trial Timeline		D0	V01+30 days	V02 + 45 days	V03 + 45 days	V04 + 30 days	V05 + 5 months	V06 + 30 days
BL	BL0001 (6 mL)					BL0002 (6 mL)		BL0003 (6 mL)
Group 3	Meningococcal Serogroups (A, C, Y, W)* Pertussis (PT, FHA)	—		—		Meningococcal Serogroups (A, C, Y, W) Hib (PRP) Pertussis (PT, FHA) HepB Polio (types 1, 2, 3) Tetanus Diphtheria PCV13		Meningococcal Serogroups (A, C, Y, W) MMR‡
Group 4	Pertussis (PT, FHA)	—	—	—	—	Pertussis (PT, FHA) HepB Polio (types 1, 2, 3) Tetanus Diphtheria PCV13		MMR

PT: pertussis toxin; FHA: filamentous hemagglutinin; Hib: *Haemophilus influenzae* type B; PRP: polyribosyl-ribitol phosphate; HepB: hepatitis B; PCV13: pneumococcal 13-valent conjugate vaccine; M-M-R®II: measles, mumps, and rubella

\*Antibody responses to meningococcal serogroups (A, C, Y, and W) will be measured by rSBA before the first vaccination, 30 days after the final vaccination in the infant series, and 30 days after the last vaccination in the entire 3- or 4- dose vaccine schedule in a subset of subjects (100 subjects per group in Groups 1, 3, and 50 subjects per group in Groups 2.)

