## 2.2 Secondary Objective

- 1) To describe the hSBA vaccine seroresponse to the antigens (meningococcal serogroups A, C, Y, and W) for Groups 1 and 2, 30 days after the last vaccination of the infant series (Dose 2 of MenACYW conjugate vaccine and Dose 3 of Menveo®), when administered concomitantly with routine pediatric vaccines in healthy infants and toddlers in Mexico
- 2) To describe the hSBA vaccine seroresponse to the antigens (meningococcal serogroups A, C, Y, and W) for Group 3, 30 days after the last vaccination of the infant series (Dose 2 of MenACYW conjugate vaccine), when administered concomitantly with routine pediatric vaccines in healthy infants and toddlers in the Russian Federation
- 3) To describe the immunogenicity profile of routine pediatric vaccines when administered concomitantly with MenACYW conjugate vaccine (Groups 1 and 3), Menveo® (Group 2), or when administered alone (Group 4)
- 4) To describe the hSBA antibody responses against meningococcal serogroups A, C, Y, and W when MenACYW conjugate vaccine and Menveo® are administered concomitantly with routine pediatric vaccines in Mexico and the Russian Federation (Groups 1, 2, and 3)
- 5) To describe the antibody titers to the antigens (meningococcal serogroups A, C, Y, and W) present in MenACYW conjugate vaccine and Menveo® measured by serum bactericidal assay using baby rabbit complement (rSBA) before the first vaccination (Visit 1) and 30 days after the last vaccination of the infant series (Dose 2 of MenACYW conjugate vaccine and Dose 3 of Menveo®), when administered concomitantly with routine pediatric vaccines in a subset of subjects (100 subjects per group in Groups 1 and 3, and 50 subjects in Group 2) in Mexico
- 6) To describe the antibody titers to the antigens (meningococcal serogroups A, C, Y, and W) present in MenACYW conjugate vaccine measured by rSBA before the first vaccination (Visit 1) and 30 days after the last vaccination of the infant series (Dose 2 of MenACYW conjugate vaccine), when administered concomitantly with routine pediatric vaccines in a subset of subjects (100 subjects in Group 3) in the Russian Federation

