#### 6.2.4.3 Dose Selection and Timing

Subjects in Groups 3 and 4 (the Russian Federation) will receive Pentaxim® administered at 3, 4.5, and 6 months of age.

#### 6.2.5 Identity of Other Product 6

**ENGERIX-B®**: (Hepatitis B Vaccine [Recombinant]) (GlaxoSmithKline Biologicals 441 Rixensart, Belgium)

**Form:** Suspension for injection

**Dose:** 0.5 mL

**Route:** IM

**Batch number:** TBD

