  - Anti-mumps antibody concentrations (serostatus cutoff:  $10 \text{ Mumps Ab units} / \text{mL}$ )
  - Anti-rubella antibody (serostatus cutoff:  $10 \text{ IU} / \text{mL}$ )
  - Anti-tetanus antibody concentrations  $\geq 0.1 \text{ IU} / \text{mL}$  and  $1.0 \text{ IU} / \text{mL}$
  - Anti-diphtheria antibody concentrations  $\geq 0.1 \text{ IU} / \text{mL}$  and  $1.0 \text{ IU} / \text{mL}$
  - Anti-pertussis (PT and FHA) vaccine responsea
  - Anti-poliovirus types 1, 2, and 3 antibody titers  $\geq 1:8$
  - Anti-PRP antibody concentrations and  $\geq 0.15 \mu\text{g} / \text{mL}$  and  $1.0 \mu\text{g} / \text{mL}$
  - Anti-HBs concentrations  $\geq 10 \text{ mIU} / \text{mL}$  and  $100 \text{ mIU} / \text{mL}$

The following serological endpoints will be described for the Russian Federation (Groups 3 and 4):

- Day 0 (before the first vaccination with Pentaxim®):
  - Anti-pertussis antibody concentrations (PT and FHA)
- 30 days after the 6-months vaccinations with Pentaxim® and ENGERIX-B®:
  - Antibody concentrations/titers for all antigens
  - Anti-tetanus antibody concentrations  $\geq 0.1 \text{ IU} / \text{mL}$  and  $1.0 \text{ IU} / \text{mL}$
  - Anti-diphtheria antibody concentrations  $\geq 0.1 \text{ IU} / \text{mL}$  and  $1.0 \text{ IU} / \text{mL}$
  - Anti-pertussis (PT and FHA) vaccine response
  - Anti-poliovirus types 1, 2, and 3 antibody titers  $\geq 1:8$
  - Anti-PRP antibody concentrations and  $\geq 0.15 \mu\text{g} / \text{mL}$  and  $1.0 \mu\text{g} / \text{mL}$
  - Anti-HBs concentrations  $\geq 10 \text{ mIU} / \text{mL}$  and  $100 \text{ mIU} / \text{mL}$
- 30 days after the 12-months vaccination with MMR:
  - Antibody concentrations for measles, mumps and rubella

---

a Pertussis vaccine response definition:

- If the pre-vaccination concentration is  $\geq 4 \times \text{LLOQ}$ , then the post-vaccination concentration is  $\geq$  pre-vaccination concentration
- If the pre-vaccination concentration is  $< 4 \times \text{LLOQ}$ , then the post-booster vaccination concentration is  $\geq 4 \times \text{LLOQ}$

- Anti-measles antibody concentrations (serostatus cutoff 225 mIU / mL)
  - Anti-mumps antibody concentrations (serostatus cutoff: 10 Mumps Ab units / mL)
  - Anti-rubella antibody (serostatus cutoff: 10 IU / mL)
- 4) The following serological endpoints will be assessed for Groups 1, 2, and 3:

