#### ***Anti-Haemophilus influenzae type b (Anti-PRP) Antibodies***

Anti-PRP concentrations will be measured using a Farr-type radioimmunoassay (RIA). Serum levels of anti-Hib Capsular PRP antibody are determined by RIA, in which serum samples are incubated with radiolabeled PRP (H-PRP) in the presence of Cl (volume marker). Specific antibody binds to tritiated capsular PS to form antigen-antibody complexes. These complexes are precipitated with ammonium sulfate and collected by centrifugation. The radioactivity is measured in the precipitated pellet, in counts per minute and is proportional to the amount of anti-Hib capsular PS antibody present in the serum sample. The concentration of anti-PRP antibody in the serum sample is determined from the concentration response curve generated by the titration results of dilutions of the reference standard analyzed in the assay. Results are reported in µg/mL by comparison to the Center for Biologics Evaluation and Research, Lot No. 1983 reference standard. The LLOQ of the anti-PRP RIA is 0.06 µg / mL.

This method will be performed on BL0003 samples collected from all subjects in Mexico. This method will be performed on BL0002 samples collected from all subjects in the Russian Federation.

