#### ***Anti-Rotavirus IgA Antibodies***

Anti-rotavirus IgA Antibodies in human serum will be measured by ELISA. Microtiter plates are coated with rabbit anti-rotavirus antibody and then viral lysate (positive wells) or control cell lysate (negative wells) is added. Diluted serum samples (test samples, reference standard, and quality controls) are incubated in the wells. Unbound antibodies are washed from the wells, and enzyme-conjugated anti-human IgA is added. The enzyme conjugate binds to the antigen-antibody complex. Excess conjugate is washed away and a specific colorimetric substrate is added. Bound enzyme catalyzes a hydrolytic reaction, which causes color development. A reference standard assayed on each plate is used to calculate the amount of specific anti-rotavirus IgA antibody in the units assigned by the reference standard (units [U] / mL of serum).

This method will be performed on BL0002 samples collected from all subjects in Mexico.

The priority of titration for subjects receiving MenACYW conjugate vaccine (Group 1) or Menveo® vaccine (Group 2), and DTaP-IPV-HB-Hib, Rotavirus, PCV13 vaccines is as follows: hSBA, anti-PT, anti-FHA, anti-Hep B, anti-PRP, anti-polio 1, 2, and 3, anti-tetanus, and anti-diphtheria, anti-pneumococcal serotypes 1, 3, 5, 6A, 7F, 19A, 4, 6B, 9V, 14, 18C, 19F, and 23F and anti-Rotavirus (IgA).

The priority of titration for subjects receiving MenACYW conjugate vaccine (Group 1) or Menveo® vaccine (Group 2), and DTaP-IPV-HB-Hib Measles, Mumps, Rubella, PCV13 vaccines is as follows: hSBA, anti-PT, anti-FHA, anti-Hep B, anti-PRP, anti-polio (types 1, 2, and 3) anti-tetanus, anti-diphtheria, anti-measles, anti-mumps, anti-rubella, anti-pneumococcal serotypes 1, 3, 5, 6A, 7F, 19A, 4, 6B, 9V, 14, 18C, 19F, and 23F.

For subjects receiving MenACYW conjugate vaccine and DTaP-IPV//Hib vaccine and hepatitis B vaccine (Group 3) the priority of titrations is as follows: hSBA, anti-PT, anti-FHA, anti-PRP, anti-polio 1, 2, and 3, anti-tetanus, anti-diphtheria and anti-HepB.

For subjects receiving DTaP-IPV//Hib and hepatitis B vaccines only (Group 4), the priority of titrations is as follows: anti-PT, anti-FHA, anti-PRP, anti-polio 1, 2, and 3, anti-tetanus, and anti-diphtheria and anti-Hep B.

For subjects receiving PCV-13 vaccine only (Group 4), the priority of titrations is as follows: anti-pneumococcal serotypes 1, 3, 5, 6A, 7F, 19A, 4, 6B, 9V, 14, 18C, 19F, and 23F.

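### Protocol Table 5.4 omits Hib (PRP) from the Group 4 sample at V05, against the endpoint, assay and titration text that requires it

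*Protocol*

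**What the plan says.** Protocol Table 5.4 gives the antigens to be tested at each Russian blood draw. At V05 (sample BL0002) the Group 3 cell reads "Meningococcal Serogroups (A, C, Y, W) Hib (PRP) Pertussis (PT, FHA) HepB Polio (types 1, 2, 3) Tetanus Diphtheria PCV13". The Group 4 cell in the next row reads only "Pertussis (PT, FHA) HepB Polio (types 1, 2, 3) Tetanus Diphtheria PCV13". The shorter string also forms the tail of the Group 3 cell, so the difference lies in what comes before it: Group 4 lacks both the meningococcal entry, as expected, and Hib (PRP).

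On dosing the two groups are alike. Protocol 6.2.4.3 states: "Subjects in Groups 3 and 4 (the Russian Federation) will receive Pentaxim ® administered at 3, 4.5, and 6 months of age". Pentaxim contains a Hib conjugate (Protocol 6.2.4.1).

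Three other places call for anti-PRP in Group 4:

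- **Endpoints.** Protocol 9.2.1.1 opens its Russian list with "The following serological endpoints will be described for the Russian Federation (Groups 3 and 4" and includes anti-PRP at 0.15 and 1.0 µg/mL, 30 days after the 6-month vaccinations. The Synopsis and SAP 4.2.1.1 agree.
- **Assay.** The anti-PRP paragraph in Protocol 9.2.1.2 states: "This method will be performed on BL0002 samples collected from all subjects in the Russian Federation". SAP 4.2.1.2 repeats this.
- **Titration order.** At the end of Protocol 9.2.1.2, and again in SAP 4.2.1.2, anti-PRP is third for Group 4: "anti-PT, anti-FHA, anti-PRP, anti-polio 1, 2, and 3, anti-tetanus, and anti-diphtheria and anti-Hep B".

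The Russian analysis lists in Protocol 12.1.2.4 and SAP 5.1.2.1.3 also include anti-PRP. The SAP does not reproduce Table 5.4.

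**The concern.** Secondary objective 3 is to describe the routine vaccines when given "concomitantly with MenACYW conjugate vaccine (Groups 1 and 3), Menveo ® (Group 2), or when administered alone (Group 4". Group 4 is there to supply the last of these. It is the only arm with no meningococcal vaccine, and the only randomized control for the Hib response after the three-dose Pentaxim series in the Russian Federation. Protocol 5.1.2 stresses that possible interference with routine vaccines has to be evaluated.

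Table 5.4 is an operative schedule from which a laboratory request could be drawn up. If it were followed as printed, the Group 3 anti-PRP rates at both thresholds and the anti-PRP geometric mean concentration would have no concurrent randomized value to be read against.

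Pentaxim's Hib polysaccharide is conjugated to tetanus protein, and MenACYW uses a tetanus toxoid carrier. That makes Hib a natural antigen to look at for interference. This step is an inference from the two compositions; the documents speak of interference only in general terms.

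**Working it through.** **Plan's own figures.** The only sizing statements (Protocol 12.5, SAP 5.5) concern adverse events. With 1 − (1 − p)^n they reproduce: 0.9503 (n = 525, p = 0.57%), 0.9496 (n = 350, 0.85%), 0.9513 (n = 200, 1.5%) and 0.9517 (n = 150, 2%). None bears on this point, which turns on a comparison of texts.

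**Is anti-PRP due in Group 4 at V05?**

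| Place | Group 3 | Group 4 |
|---|---|---|
| Protocol Table 5.4 | yes | no |
| Endpoint list, Protocol 9.2.1.1 and SAP 4.2.1.1 | yes | yes |
| PRP assay paragraph, Protocol 9.2.1.2 and SAP 4.2.1.2 | yes | yes |
| Titration order, same sections | yes | yes |

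No passage gives a reason to leave Group 4 out. Blood volume does not supply one: both groups give 6 mL at V05, and Group 4 has no meningococcal assay to share the serum with.

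**Could Mexico stand in?** Group 2 also receives no MenACYW and has anti-PRP measured. But it receives Menveo, its Hib vaccine is Hexacima given at 2, 4, 6 and 12 months, and Table 5.3 tests Hib (PRP) only at V06 (13 months), not at V04 (7 months). It therefore cannot replace Group 4 for the 7-month Pentaxim response.

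**Worst-case count.** Planned sizes are 150 in Group 3 and 75 in Group 4 (Protocol 6.5). Under the endpoint and assay text there are up to 150 and up to 75 anti-PRP results at V05. Under Table 5.4 as printed there are up to 150 and 0.

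**What the 75 results would provide.** The documents give no expected anti-PRP rate. Assume 70% to 95% above a threshold and no attrition. The plan's method for proportions is the exact 95% interval. The last column is an illustration only, since the plan specifies no difference: half-width = 1.96 × √[p(1 − p)(1/150 + 1/75)].

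| Assumed p | Group 4 result | Exact 95% CI | Half-width, Group 3 − Group 4 |
|---|---|---|---|
| 70% | 52/75 (69.3%) | 57.6–79.5% | 12.7 points |
| 80% | 60/75 (80.0%) | 69.2–88.4% | 11.1 points |
| 90% | 68/75 (90.7%) | 81.7–96.2% | 8.3 points |
| 95% | 71/75 (94.7%) | 86.9–98.5% | 6.0 points |

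So the Group 4 arm gives a usable, if coarse, reference. Without it there is none.

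**A second conflict in the same cells.** Both Russian V05 cells list PCV13. Footnotes in Protocol 5.1.1, 12.1.2.4 and SAP 5.1.2.1.3 say that pneumococcal responses are not measured in the Russian Federation. Yet the anti-pneumococcal assay paragraph covers BL0002 from all groups, and a pneumococcal titration order is given for Group 4. This conflict therefore reaches beyond the table.

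**The case against.** The strongest reply is that nothing will be lost. Every other place that deals with the matter includes Group 4, and the SAP carries the endpoint, the assay instruction and the titration order without the table. The omission looks like a line missed in one cell, and a laboratory working from the assay text would run the test. Most of this stands. It makes the point an inconsistency and not a design decision, and 150 against 0 is a worst case, not an expected loss. It does not remove the need for a correction: no text says which place takes precedence, and SAP 5.7 corrects another protocol error (the measles cutoff) while leaving this one.

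A reader might go further and infer that the study would have no MenACYW-free Hib control at all. The documents do not support that, because Group 2 is MenACYW-free and has a 13-month anti-PRP result. Nor does the delayed release of PRP data in SAP 5.7 suggest that Group 4 was skipped; it defers PRP to the final analysis and excludes no group.

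The analyses are descriptive with no hypothesis, so no test or power is affected. Finally, a table line lost in converting the PDF cannot be wholly excluded, although the row shows no sign of breakage.

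**Conclusion.** The inconsistency is real and should be corrected. Table 5.4 omits Hib (PRP) for Group 4 at V05, in conflict with the endpoint list, the PRP assay instruction and the Group 4 titration order in both documents. What is exposed is the only randomized control for the post-primary Pentaxim Hib response in the Russian Federation: at worst 0 of 75 Group 4 results beside up to 150 in Group 3.

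That size assumes full enrollment, no attrition and a laboratory that works from the table. The documents do not show that Group 4 testing was deliberately dropped, or that it has been or will be missed.

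**What to change.** 1. Add Hib (PRP) to the Group 4 V05 cell of Table 5.4, or state that the endpoint list and PRP assay paragraph govern. The table edit is cleaner: a general rule that assay text prevails would settle PRP but not PCV13.
2. In the same edit, reconcile the PCV13 entries in both Russian V05 cells, the anti-pneumococcal assay paragraph and the Group 4 pneumococcal titration order with the statements that pneumococcal antibodies are not determined in the Russian Federation.
3. Before the final database lock described in SAP 5.7, confirm that the assay request includes anti-PRP on Group 4 BL0002. At that stage this is the step that protects the data; the table edit mainly corrects the record. Note the correction in SAP 5.7 beside the measles cutoff.

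The cost is a small text edit and one check with the laboratory. If the check shows that Group 4 was not requested, up to 75 further anti-PRP tests would be needed, provided serum remains. Protocol 7.4 allows Russian sera to be used for testing directly related to this study. The documents give no budget, so the cost of those tests cannot be judged from them.

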### ***Collection of Safety Data***

All subjects will be followed for safety from Visit 1 to the last study visit.

- All subjects will be observed for 30 minutes after vaccination under the supervision of a responsible healthcare professional at each study site and any unsolicited systemic AEs occurring during that time will be recorded as immediate unsolicited systemic AEs in the electronic case report form (eCRF).
- The subject's parent / guardian will record information in a diary card about solicited injection-site reactions and solicited systemic reactions from D0 to D7 after each vaccination and unsolicited AEs will be recorded from D0 after each vaccination until the subject returns for the next study visit.
- Serious AEs (including AEs of special interest [AESIs]) will be recorded in a diary card throughout the study. The subject's parent / guardian will be asked to notify the site immediately about any potential SAEs at any time during the trial.
- A member of the study staff will contact subject's parent / guardian by telephone 8 days (+2 days) after each vaccination visit to identify the occurrence of any SAE (including AESIs) not yet reported and to remind them to complete the diary card after each vaccination visit, and to bring it back to the next study visit.
- The completed diary cards will be collected and reviewed with the subject's parent / guardian at subsequent visits.
- A member of the study staff will contact the subject's parent / guardian by telephone 14 days (+2 days) before the first study visit of the subject's second year of life to identify the occurrence of any SAE not yet reported and to remind them to complete the diary card and to bring it back to the next study visit so it can be reviewed at the study site.

